3.3.3 Exclusion criteria

Subjects will not be allowed to participate, if any of the following general criteria apply:

1. Any finding in the medical examination (including BP, PR or ECG) deviating from normal and assessed as clinically relevant by the investigator
2. Repeated measurement of systolic blood pressure outside the range of 90 to 140 mmHg, diastolic blood pressure outside the range of 50 to 90 mmHg, or pulse rate outside the range of 50 to 90 bpm
3. Any laboratory value outside the reference range that the investigator considers to be of clinical relevance
4. Any evidence of a concomitant disease assessed as clinically relevant by the investigator
5. Gastrointestinal, hepatic, renal, respiratory, cardiovascular, metabolic, immunological or hormonal disorders
6. Cholecystectomy or other surgery of the gastrointestinal tract that could interfere with the pharmacokinetics of the trial medication (except appendectomy or simple hernia repair)
7. Diseases of the central nervous system (including but not limited to any kind of seizures or stroke), and other relevant neurological or psychiatric disorders

Proprietary confidential information © 2019 Boehringer Ingelheim International GmbH or one or more of its affiliated companies

8. History of relevant orthostatic hypotension, fainting spells, or blackouts
9. Chronic or relevant acute infections
10. History of relevant allergy or hypersensitivity (including allergy to the trial medication or its excipients)
11. Use of drugs within 30 days of planned administration of trial medication that might reasonably influence the results of the trial (including drugs that cause QT/QTc interval prolongation)
12. Intake of an investigational drug in another clinical trial within 90 days or within 5 half-lives, whichever is longer, of planned administration of investigational drug in the current trial, or concurrent participation in another clinical trial in which investigational drug is administered
13. Alcohol abuse (consumption of more than 30 g per day for males) within the 24 months prior to dosing
14. Drug abuse within the 24 months prior to dosing or positive drug screening
15. Blood donation of more than 100 mL within 30 days of planned administration of trial medication or intended blood donation during the trial
16. Intention to perform excessive physical activities within one week prior to the administration of trial medication or during the trial
17. Inability to comply with the dietary regimen of the trial site
18. A marked baseline prolongation of QT/QTc interval (such as QTc intervals that are repeatedly greater than 450 ms) or any other relevant ECG finding at screening
19. A history of additional risk factors for *Torsade de Pointes* (such as heart failure, hypokalaemia, or family history of Long QT Syndrome)
20. Subject is assessed as unsuitable for inclusion by the investigator, for instance, because the subject is not considered able to understand and comply with study requirements, or has a condition that would not allow safe participation in the study

In addition, the following trial-specific exclusion criteria apply:

21. Structural brain abnormality has been shown on an MRI
22. Severe anxiety of enclosed spaces
23. Contraindication for arterial cannulation: Allen's test indicating potential risk in placement of the arterial cannula.
24. Contraindication to MRI as determined by screening and safety questionnaire including but not limited to significant tattoos (as determined by the radiographer), cardiac pacemakers, aneurysm clips and cochlear implants.
25. Unable to lie flat on the MRI or PET scanner for a prolonged period of time.
26. Prior participation in other research protocols in the past year such that the total effective dose including this study would exceed 10 mSv.

For study restrictions, refer to [Section 4.2.2.](#)

3.3.4 Withdrawal of subjects from treatment or assessments

Subjects may discontinue trial treatment or withdraw consent to trial participation as a whole ('withdrawal of consent') with very different implications; please see [Sections 3.3.4.1](#) and [3.3.4.2](#) below.

If a subject is removed from or withdraws from the trial prior to the first administration of trial medication, the data of this subject will not be entered in the case report form (CRF) and will not be reported in the clinical trial report (CTR). If a subject is removed from or withdraws from the trial after the first administration of trial medication, this will be documented and the reason for discontinuation must be recorded in the CRF; in addition, the data will be included in the CRF and will be reported in the CTR. At the time of discontinuation, a complete end of trial examination will be performed, if possible, and the information will be recorded in the CRF. If the discontinuation occurs before the end of the REP (see [Section 1.2.2](#)), the discontinued subject should if possible be questioned for AEs and concomitant therapies at or after the end of the REP in order to ensure collection of AEs and concomitant therapies throughout the REP, if not contrary to any consent withdrawal of the subject.

3.3.4.1 Discontinuation of trial treatment

An individual subject will discontinue trial treatment if:

1. The subject wants to discontinue trial treatment, without the need to justify the decision
2. The subject has repeatedly shown to be non-compliant with important trial procedures and, in the opinion of both the investigator and sponsor representative, is not willing or able to adhere to the trial requirements in the future.
3. The subject needs to take concomitant medication that interferes with the investigational medicinal product or other trial treatment
4. The subject can no longer receive trial treatment for medical reasons (such as surgery, adverse events [AEs], or diseases)
5. The subject has an elevation of AST and/or ALT ≥ 3 -fold ULN and an elevation of total bilirubin ≥ 2 -fold ULN (measured in the same blood sample) and/or needs to be followed up according to the DILI checklist provided in the ISF
6. In addition to these criteria, the investigator may discontinue subjects at any time based on his or her clinical judgment.

Even if the trial treatment is discontinued, the subject remains in the trial and, given his/her agreement, will undergo the procedures for early treatment discontinuation and follow up as outlined in the [Flow Chart](#) and [Section 6.2.3](#).

3.3.4.2 Withdrawal of consent to trial participation

Subjects may withdraw their consent to trial participation at any time without the need to justify the decision. If a subject wants to withdraw consent, the investigator should be involved in the discussion with the subject and explain the difference between trial treatment

Proprietary confidential information © 2019 Boehringer Ingelheim International GmbH or one or more of its affiliated companies

discontinuation and withdrawal of consent to trial participation, as well as explain the options for continued follow up after trial treatment discontinuation, please see [Section 3.3.4.1](#) above

3.3.4.3 Discontinuation of the trial by the sponsor

Boehringer Ingelheim reserves the right to discontinue the trial at any time for any of the following reasons:

1. Failure to meet expected enrolment goals overall or at a particular trial site
2. New toxicological findings, serious adverse events, or any safety information invalidating the earlier positive benefit-risk-assessment. More specifically, the trial will be terminated if more than 50% of the subjects have drug-related and clinically relevant adverse events of moderate or severe intensity, or if at least 1 drug-related serious adverse event is reported
3. Violation of GCP, or the CTP, or the contract with BI impairing the appropriate conduct of the trial
4. The sponsor decides to discontinue the further development of the investigational product
5. The investigator / trial site will be reimbursed for reasonable expenses incurred in case of trial termination (except if item 3 applies).
6. Severe non-serious adverse reactions (i.e. severe non-serious adverse events considered as, at least, possibly related to the IMP administration) in two subjects in the same dose group, independent of within or not within the same system-organ-class.

3.3.5 Replacement of subjects

In case a subject does not complete the trial, the Clinical Trial Leader together with the Trial Pharmacokineticist and the Trial Statistician are to decide, if this subject will be replaced. Replacement of subjects should always be done in mutual agreement with the principal investigator. A replacement subject will be assigned a unique trial subject number, and will be assigned to the same treatment as the subject replaces.

4. TREATMENTS

4.1 INVESTIGATIONAL TREATMENTS

The investigational product has been manufactured by BI Pharma GmbH & Co. KG. BI 1467335 doses will be calculated as a free base of the BI 1467335 salt, with 10 mg BI 1467335 free base equals to 11.3 mg BI 1467335 HCl salt and 3 mg BI 1467335 free base equals to 3.39 mg BI 1467335 HCl salt.

[¹¹C]-L-deprenyl-D2 will be administered as a solution for injection and will be manufactured by

4.1.1 Identity of the Investigational Medicinal Product

The characteristics of the test products are given below:

Substance: BI 1467335

Pharmaceutical formulation: Film-coated tablet

Source: BI Pharma GmbH & Co. KG, Germany

Unit strength: 5 mg /1 mg

Posology: 2-0-0 / 3-0-0

Route of administration: oral

Duration of use: 28 days / 42 days

4.1.2 Identity of the Non Investigational Medicinal Product

The characteristics of the NIMP are given below:

Substance: [¹¹C]-L-deprenyl-D2

Pharmaceutical formulation: Solution for injection

Source:

Unit strength: ≤100 µg

Route of administration: i.v.

Duration of use: A single dose on 3 different days during study conduct

4.1.3 Selection of doses in the trial

The doses of BI 1467335 selected for this trial are the standard clinical doses (see [Section 1.2](#)).

4.1.4 Method of assigning subjects to treatment groups

This trial is an open-label, non-randomized, parallel-group, multiple dose study.

Prior to the screening visit, subjects will be contacted in writing and informed about the planned visit dates. The subjects willing to participate can choose convenient visit dates on a first-come, first-served basis: as soon as 5 subjects have been allocated to 1 of the 2 dose groups, the following subjects will be allocated to the other dose group. Therefore, the allocation of subjects to dose groups is not influenced by trial personnel, but only by the subjects' temporal availability. As the study includes healthy male subjects from a homogenous population, relevant imbalances between the dose groups are not expected.

Within the dose group, numbers of the randomization list will be allocated to subjects in their order of registration for the study (assignment to dose group according to subjects' temporal availability). Once a subject number has been assigned, it cannot be reassigned to any other subject.

4.1.5 Drug assignment and administration of doses for each subject

This trial is a parallel-group multiple dose study. All subjects will receive the treatments in an open-labelled fashion. The treatments to be evaluated are outlined in [Table 4.1.5: 1](#) below.

Table 4.1.5: 1 Dosage and treatment schedule

Treatment	Substance	Formulation	Unit strength	Dosage
T (Test)	BI 1467335	Film-coated tablet	10 mg	2 tablets (5 mg) qd for 28 days
T (Test)	BI 1467335	Film-coated tablet	3 mg	3 tablets (1 mg) qd for 42 days

The investigator (or authorised designee) will administer the trial medication as an oral dose together with about 240 mL of water to subjects who are in a sitting position. For drug administration, the so-called four-eye principle (two-person rule) should be applied. For this, one authorised employee of the trial site should witness the administration of trial medication, and – if applicable – its preparation (e.g. reconstitution), if correct dosage cannot be ensured otherwise.

[¹¹C]-L-Deprenyl-D2 will be administered as an intravenous bolus injection for a predose assessment (between Day -14 to Day -2) and about 1,5 h after dosing of BI 1467335 on Day 14 (10 mg dose group only), Day 28 and Day 42 (3 mg dose group only).

4.1.6 Blinding and procedures for unblinding

This Phase I trial will be handled in an open fashion throughout (that is, during the conduct, including data cleaning and preparation of the analysis). This is considered acceptable because the potential for bias seems to be low and does not outweigh practical considerations.

Emergency envelopes will not be provided, because the dose of trial medication is known to investigators and subjects.

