3.2 DISCUSSION OF TRIAL DESIGN, INCLUDING THE CHOICE OF CONTROL GROUP

The doses selected for this study, 10 mg BI 1467335 q.d. (2 film-coated tablets of 5 mg dose strength) and 3 mg BI 1467335 q.d. (3 film-coated tablets of 1 mg dose strength), have been used in healthy volunteers and shown to be well tolerated. The predose measurement will be used as a baseline, so no placebo dose is required in this study.

The planned dosing duration of 28 days for the 10 mg dose group and 42 days for the 3 mg dose group is long enough to reliably achieve steady-state drug exposures and to exclude any transient effects.

Due to the time dependent non-linear kinetics of BI 1467335, systemic exposures on Day 28 and Day 42 cannot be predicted from Day 1 kinetics (IB [[c04751792](#)]). Therefore the MAO-B inhibition in the brain will be determined on Day 28 and Day 42 after start of treatment

Proprietary confidential information © 2019 Boehringer Ingelheim International GmbH or one or more of its affiliated companies

with 10 mg and 3 mg BI 1467335, respectively, and compared to the individual baseline value to investigate the maximum inhibition. The *in vitro* data suggested an irreversible inhibition, which could potentially accumulate over time following multiple dosing and with the increase in exposure observed over time which characterizes BI 1467335 kinetics. The investigation on Day 14 for the 10 mg dose group and on Day 28 for the 3 mg dose group will evaluate whether the MAO-B inhibition reaches its maximum over the treatment duration and is maintained regardless of the increase in BI 1467335 systemic exposure. The 10 mg dose group will be investigated first. In the event no MAO-B inhibition is seen following the administration of 10 mg BI 1467335 daily over 28 days, the study will be considered as complete and no further investigation with a lower dose (3 mg) will be conducted.

[¹¹C]-L-deprenyl-D2 is a PET radioligand used for measurement of the MAO-B activity in the brain. This radioligand has been used for several PET studies to evaluate MAO-B inhibition in the brain in healthy subjects and is unlikely to exhibit any detectable isotope effects (see [Section 1.4](#)).

Because of the exposure with radioligands the study will only include male subjects.

The open-label treatment is not expected to bias results, since the study endpoints are derived from medical procedures and laboratory assessments with an unlikely relevant impact by subjective factors.

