Plasma concentration data and parameters of a subject which is flagged for exclusion will be reported with its individual values but will not be included in the statistical analyses.

Descriptive statistics of PK parameters will be based on the PKS.

Only concentration values within the validated concentration range and actual sampling times will be used for the calculation of pharmacokinetic parameters. Concentrations used in the pharmacokinetic calculations will be in the same format provided in the bioanalytical report, (that is, to the same number of decimal places provided in the bioanalytical report).

Biomarkers

All scans for which good quality PET emission and arterial plasma radioligand concentration data will be obtained, will be included in the analysis.

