7.3.1 Primary endpoint analyses

Image analysis will be used to generate the outcome parameter for the PET data (proportional to the target availability at each PET scan), using the PET emission and the metabolite corrected arterial plasma input function, within an appropriate kinetic model. Tissue time-activity curves (TACs) for each region of interest (ROI) will be analysed together with arterial blood data, processed to generate metabolite-corrected arterial plasma input function curves. Kinetic modelling techniques will then be applied to the input function and TAC data to estimate parameters relating to the level of target availability for each PET scan. For scans

Proprietary confidential information © 2019 Boehringer Ingelheim International GmbH or one or more of its affiliated companies

following 14, 28 or 42 days of dosing with BI 1467335, fractional occupancy values will be generated for each post-dose PET scan by comparing the outcome parameters for baseline and post-dose scans for a subject (primary endpoint). In addition to the individual values, descriptive statistics per dose group will be provided.

The occupancy data will be related to the plasma concentration of BI 1467335 at the time of the PET scan.

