## 7.4 PRIMARY ENDPOINT

**CTP Section 7.3.1:** *Image analysis will be used to generate the outcome parameter for the PET data (proportional to the target availability at each PET scan), using the PET emission and the metabolite corrected arterial plasma input function, within an appropriate kinetic model. Tissue time-activity curves (TACs) for each region of interest (ROI) will be analysed together with arterial blood data, processed to generate metabolite-corrected arterial plasma input function curves. Kinetic modelling techniques will then be applied to the input function and TAC data to estimate parameters relating to the level of target availability for each PET scan. For scans following 14, 28 or 42 days of dosing with BI 1467335, fractional occupancy values will be generated for each post-dose PET scan by comparing the outcome parameters for baseline and post-dose scans for a subject (primary endpoint).*

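### PET analysis is not masked to scan order, while the kinetic model, outcome parameter and scan-quality criteria are unspecified and the open 10 mg result decides whether the 3 mg group runs

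*Protocol*

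**What the plan says.** - **Openness.** Protocol 4.1.6: "This Phase I trial will be handled in an open fashion throughout (that is, during the conduct, including data cleaning and preparation of the analysis". The reason given there is: "This is considered acceptable because the potential for bias seems to be low and does not outweigh practical considerations". Protocol 3.2 adds that open treatment should not bias the results, "since the study endpoints are derived from medical procedures and laboratory assessments with an unlikely relevant impact by subjective factors".
- **Deriving the primary endpoint.** Protocol 7.3.1 obtains a value for each scan "using the PET emission and the metabolite corrected arterial plasma input function, within an appropriate kinetic model". SAP 7.4 repeats the protocol text: "Kinetic modelling techniques will then be applied to the input function and TAC data to estimate parameters relating to the level of target availability". Neither document names the model or the parameter.
- **Region.** Protocol 7.3.1 refers to regions of interest without listing them. SAP 5.1 and 5.2.2 state that the primary and secondary PET endpoints refer to the whole brain.
- **Which scans count.** Protocol 7.3, under Biomarkers: "All scans for which good quality PET emission and arterial plasma radioligand concentration data will be obtained, will be included in the analysis". No criteria follow, there or in the SAP. SAP 6.2 also allows exclusion from the PET set for certain procedural or timing violations, decided at the Report Planning Meeting at the latest.
- **What depends on the result.** Protocol 7.4 plans a preliminary analysis of MAO-B inhibition once the 10 mg group is complete. Under Protocol 1.3, 3.1 and 3.2 the 3 mg group is dropped if no inhibition is seen. No threshold is given.

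**The concern.** The case for open handling is that subjective factors hardly matter. That suits a fixed assay better than this endpoint. The percentage reduction comes from a chain of analytic steps: metabolite-corrected input function, whole-brain tissue curve, kinetic model, and a decision on whether each scan is usable. The plan leaves the model, the outcome parameter and the usability rule to be settled later, and describes no step that hides from the analyst which scan is baseline.

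The combination is what matters. Open analysis is tolerable when the model and the quality rule are fixed beforehand. Unfixed choices are tolerable when the person making them is masked. As written, the plan has neither safeguard.

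At stake are the primary endpoint in groups of 5 and the decision to run the 3 mg group. A small apparent inhibition is the case in which a model or quality choice could tip the reading of whether any inhibition was seen. It is also the case in which masking works best, because the on-drug scan does not give itself away.

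**Working it through.** **1. Is there a planned figure to reproduce?** No. Protocol 7.7 gives 5 subjects per dose group, chosen for practical reasons, with no precision or power calculation, and Protocol 7.2 plans no confirmatory test. No SD of the percentage reduction appears in either document. The check is mainly a comparison of sections.

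**2. Sections side by side.**

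| Analytic choice | Fixed in the plan? | Where |
|---|---|---|
| Region for PET endpoints | Yes, whole brain | SAP 5.1, 5.2.2 |
| How the whole-brain value is formed (one curve or combined regions; delineation) | No | Protocol 7.3.1, SAP 7.4 |
| Kinetic model | No: "within an appropriate kinetic model" | Protocol 7.3.1, repeated in SAP 7.4 |
| Outcome parameter | No | Protocol 7.3.1, SAP 7.4 |
| Scan-quality criteria | No | Protocol 7.3 |
| Masking of the analyst to scan order | Not described | Protocol 4.1.6, 7.3.1; SAP 7.4 |

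**3. What one rejected scan does.** Each subject has one planned baseline scan and two on-treatment scans, so 3 × 5 = 15 scans per group.
- Rejecting a baseline scan leaves nothing to compare with, so the subject drops out of all PET endpoints: 1/5 = 20% of the group.
- Rejecting the last-day scan removes that subject's primary value, although the subject stays in the PET set under SAP 6.3 through the earlier on-treatment scan.

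**4. Scale of losing one extreme value.** Assume normally distributed percentage reductions with between-subject SD s.
- Mean of the remaining four, minus mean of all five = (mean − minimum)/4.
- The expected minimum of 5 standard normal values is −1.163 (1,000,000 simulated samples).
- Expected shift = 1.163 s/4 = 0.29 s upwards. By symmetry, dropping the highest value shifts the mean 0.29 s downwards.

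| Assumed s (points) | Shift in group mean (points) |
|---|---|
| 5 | 0.291 × 5 = 1.5 |
| 10 | 0.291 × 10 = 2.9 |
| 15 | 0.291 × 15 = 4.4 |

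**5. Comparison with sampling error.** The 95% interval half-width is t(0.975, n−1) × s/√n, which is 1.24 s for n = 5 and 1.59 s for n = 4. The shift is 0.29/1.24 = 0.23 of the half-width at n = 5.

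The effect of switching kinetic model is not quantified, because the documents give nothing from which to calculate it.

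**The case against.** The strongest reply is that the missing items are a matter of pre-specification. Once the model, outcome parameter and quality criteria are written down, most of the discretion is gone and masking adds less. The trial is exploratory and descriptive, each subject is his own control, individual lines and medians are plotted (SAP 7.4.1), and platelet MAO-B gives supporting evidence (Protocol 5.8). The sponsor also considered bias and gave reasons. All of this stands, and it is why the point ranks low. It does not remove the point: the items are not written down, and even written quality criteria need a judgement scan by scan.

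A reader might infer stronger claims that the documents do not support:
- **That regions are left to the analyst.** SAP 5.1 and 5.2.2 fix the whole brain. Only its derivation is open. The SAP is dated 17 January 2020, and the documents do not show whether that came before or after the 10 mg preliminary analysis.
- **That Protocol 4.1.6 expressly makes image reading open.** It does not mention image analysis. Open reading is inferred from its scope and from the absence of any masking step. The synopsis text naming who analyses the images has a gap, so that party's own procedures cannot be seen.
- **That the choices could not be audited.** Individual values are listed (SAP 7), important deviations are listed (SAP 6.2), and source-data changes must be traceable (Protocol 8.3.1).
- **That the sponsor wants a negative answer.** The synopsis speaks of excluding clinical relevance, but in the same sentence of identifying and quantifying inhibition.
- **That masking to dose would help at the first read-out.** Only the 10 mg group exists then, so only scan order can be hidden.

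The missing go/no-go threshold is a separate matter that masking does not cure.

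**Conclusion.** The point holds in a limited form. No masking of the PET analyst to scan order is described, the kinetic model and outcome parameter are unnamed, the scan-quality rule has no criteria, and the whole-brain derivation is unstated. These choices can be made with baseline and on-drug scans identified, and the resulting 10 mg value decides whether the 3 mg group runs.

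The only figure available is a scale: about 0.29 SD, or 1.5 to 4.4 points. It rests on normality, on an assumed SD of 5 to 15 points, and on the lost scan being exactly the most extreme of five. It should not be read as the bias expected from unmasked analysis, and it is less than a quarter of the interval half-width at n = 5.

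Nothing here shows that bias would occur or that the trial could not meet its aim. The change is worth making because it costs little and protects the primary endpoint and the decision on the second group. Rating: nice to have.

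**What to change.** Keep dosing open. Amend Protocol 4.1.6 and 7.3.1, with matching text in SAP 7.4, as follows:

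1. Data management passes scans and arterial data to the existing image analyst under codes, grouped by subject and in scrambled order, without date or scan day. Dose is withheld as well once both groups exist.
2. Before decoding, the analyst fixes the kinetic model, the way the whole-brain value is derived, and a pass/fail quality call for each scan.
3. The outcome parameters are locked. Only then are the codes opened and the percentage reductions calculated.
4. The same sequence is followed separately for the 10 mg preliminary analysis, where masking applies to scan order only.

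Naming the model, the outcome parameter and the quality criteria in the SAP beforehand would strengthen this further.

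**Cost.** One coding and decoding step and a short delay at the 10 mg read-out, with no extra scans and no added burden for subjects. Because the party doing the image analysis cannot be seen in the documents, that no extra reader is needed is an assumption to confirm. Masking covers image processing only: subjects take their daily dose at the PET site on scan days (Protocol 5.5.1), so staff acquiring the scans will know. It will also be imperfect if inhibition is near complete, which is when it matters least.
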